2. OBJECTIVES AND ENDPOINTS

This study will evaluate the potential placental transfer of ocrelizumab in women with CIS or MS (in line with the locally approved indications) whose last dose of ocrelizumab was administered anytime from 6 months before the LMP through to the first trimester of pregnancy (up to gestational Week 13), and the corresponding pharmacodynamic effects, particularly B-cell levels, in the infants.

Specific objectives and corresponding endpoints for the study are outlined below.

Table 1 Objectives and Corresponding Endpoints

Objectives	Corresponding Endpoints
Primary Outcome Measure	
• To evaluate whether infants potentially exposed to ocrelizumab during pregnancy present with postpartum B-cell depletion	 Proportion of infants with B-cell levels (CD19 + cells, absolute counts) below the LLN, measured at Week 6 of life

ASQ-3 = Ages and Stages Questionnaire, version 3; EDSS = Expanded Disability Status Scale; HBV = hepatitis B virus; Hib = Hemophilus influenzae type b; LLN = lower limit of normal; MMR = measles, mumps, and rubella; MS = multiple sclerosis; PCV-13 = 13-pneumococcal conjugate vaccine; SARS-CoV-2 = severe acute respiratory syndrome coronavirus 2; sNfl = serum neurofilament light chain; WHO = World Health Organization.

Table 1 Objectives and Corresponding Endpoints (cont.)

Objectives	Corresponding Endpoints	
Secondary Outcome Measures		
To evaluate B-cell levels in infants potentially exposed to ocrelizumab during pregnancy	 B-cell levels (CD19 + cells, absolute counts and percentage of lymphocytes) measured at Week 6 of life 	
• To evaluate whether there is placental transfer of ocrelizumab from the mother to the infant	• Serum concentration of ocrelizumab in the umbilical cord blood at birth (target time frame of blood sampling: within 1 hour after delivery)	
	 Serum concentration of ocrelizumab in the infant at Week 6 of life 	
To evaluate whether infants potentially exposed to ocrelizumab during pregnancy are able to mount humoral immune responses to clinically relevant vaccines	• Mean titers of antibody immune response(s) to common childhood vaccinations with full or partial doses given prior to 1 year, which include responses to diphtheria, tetanus, pertussis , Hib, PCV-13, MMR, and HBV	
	 Proportion of infants with positive humoral response (seroprotective titers; as defined for the individual vaccine) to vaccines 	

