3.1.4 Vaccination Period

Both the mother and the infant will enter an extension phase, which will continue approximately until the infant reaches 13 months of age. This is designed to evaluate whether infants potentially exposed to ocrelizumab during pregnancy are able to mount humoral immune responses to clinically relevant vaccines.

Infant laboratory assessments will be performed 1 month (+30 days) after the first dose of MMR vaccine (if first dose is administered at 11 months of age or later) or 1 month (+30 days) after second dose of MMR vaccine (if first dose is administered before 11 months of age), or at Month 13 of chronological age (+30 days), if MMR vaccine is not planned to be administered (as per local clinical practice, vaccinations may include diphtheria, tetanus, pertussis, Hemophilus influenzae type b [Hib], 13-valent pneumococcal conjugate vaccine [PCV-13], hepatitis B virus [HBV], and MMR). Additionally, infants will continue to be followed up for growth (age-adjusted body length, weight and head circumference) and developmental milestones up to 12 months of age. Growth charts following the World Health Organization (WHO) Child Growth Standards (WHO 2022), absolute values and the Ages and Stages Questionnaire, version 3 (ASQ-3) will be used; other standard measurements recorded by e.g., the pediatrician as part of routine postnatal care may also be used. The time windows for infant growth velocity and child developmental milestone assessments are given in Appendix 6. Post-natal timings of ocrelizumab infusions every 6 months and laboratory/clinical assessments in the mother may occur at different time points than infant assessments. In case the mother decides to switch to another DMT or to stop DMT after birth, no laboratory/clinical assessments will be performed for the mother. However, the infant blood sample 1 month (+30 days) after the first or second dose of MMR vaccine (or at Month 13 of age [+30 days]) will still be collected.

A structured telephone interview will be conducted by site personnel postpartum every 3 months (in-between ocrelizumab infusions) for a general review, and to identify and collect information on any changes in the woman's or infant's health status (including the occurrence of MS relapses in the woman and use of new concomitant medications) and possible adverse events in both the woman and the infant (particularly infections);

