4.5.4 Infant Vaccination Schedule

Infants will receive vaccinations according to the immunization schedule recommended in each participating country. The safety and timing of vaccination of the infant should still be discussed with the mother, in particular the vaccination with live-attenuated vaccines (e.g., MMR) for which the results on B-cell levels at Week 6 of life may be informative. Vaccines administered from birth throughout the end of the study, should be recorded at Months 2, 4, 6, 9, and 12 as well as at 1 month (+30 days) after first or second MMR dose/Month 13 of age (+30 days) and may include *diphtheria, tetanus, pertussis*, Hib, PCV-13, HBV, and MMR.

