- For Month 13 of age (+30 days)/1 month (+30 days) after the first or second dose of MMR: all efforts will be made to collect samples. However, if they cannot be collected, this will not be considered a protocol deviation.
- ^{mm} Vaccinations may include the following, in line with clinical practice: *diphtheria, tetanus, pertussis*, Hib, PCV-13, HBV, and MMR. Antibody responses to vaccinations will be measured 1 month (+30 days) after the first dose of MMR vaccine (if first dose is administered at 11 months of age or later), or 1 month (+30 days) after second dose of MMR vaccine (if first dose is administered before 11 months of age), or at Month 13 of chronological age (+30 days) if MMR vaccine is not planned to be administered.

- ⁿⁿ A structured telephone interview will be conducted by site personnel postpartum every 3 months (in-between ocrelizumab infusions) for a general review, and to identify and collect information on any changes in the woman's or infant's health status (including the occurrence of MS relapses in the woman and use of new concomitant medications) and possible adverse events in both the woman and the infant (particularly infections); women will also be asked if the ASQ-3 form is being filled out. No telephone contact is needed in weeks where the woman is performing on-site visits.
- ^{oo} Adverse events in both the mother and the infant will be reported throughout the study as per standard pharmacovigilance procedures.

Table A2-1 List of Potentially Teratogenic Drugs ^a

Group	Name	ATC- Code	The Former ADEC	The FASS	Pregnancy Classification of the FDA
Anti-infective and Anti-parasitic agents	Albendazole	P02CA03	D	n.a.	С
	Amikacin	J01GB06	D	D	D
	Artemether	P01BE52	D	n.a.	С
	Artemether	P01BE02	D	n.a.	С
	Chloroquine	P01BA01	D	B3	n.a.
	Cidofovir	J05AB12	D	D	С
	Demeclocycline	J01AA01	D	n.a.	D
	Doxycycline	A01AB22	D	n.a.	D
	Doxycycline	J01AA02	D	D	D
	Efavirenz	J05AG03	D	D	D
	Fluconazole	J02AC01	D	B3	С
	Ganciclovir	J05AB06	D	D	С
	Gentamicine	J01GB03	D	D	D
	Hydroxychloroquine	P01BA02	D	B3	n.a.
	Minocycline	J01AA08	D	n.a.	D
	Netilmicin	J01GB07	D	D	D
	Oxytetracycline	J01AA06	D	D	n.a.
	Primaquine	P01BA03	D	n.a.	n.a.
	Quinine	P01BC01	D	D	С
	Ribavirin	J05AB04	D	D	Х

Group	Name	ATC- Code	The Former ADEC	The FASS	Pregnancy Classification of the FDA
	Streptomycine	J01GA01	n.a.	n.a.	D
	Tetracycline	A01AB13	D	n.a.	D
	Tetracycline	J01AA07	D	D	D
	Tigecycline	J01AA12	D	D	D
	Tobramycin	J01GB01	D	B3	D
	Valganciclovir	J05AB14	D	D	С

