4.1.5 Antibody Immune Response Analysis Set (Infants)

The antibody immune response analysis set of infants (AIRI) will include all infants in the SAFI for whom any serum titers of antibody immune response to vaccinations are available. This analysis set will be used to analyze humoral immune responses to common childhood immunizations.

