4.5.3 Infant Absolute Antibody Immune Response

The infant's antibody (Immunoglobulin [Ig]G) immune response to common childhood immunizations with full or partial doses given prior to 1 year may include (but is not limited to) responses to MMR, diphtheria, tetanus, and pertussis (DTaP), Hemophilus influenzae type b (Hib), hepatitis B virus (HBV) and 13-valent pneumococcal conjugate vaccine (PCV-13), measured 1 month after the first or second dose of MMR vaccine or at Month 13 of age (+30 days) in case MMR vaccine is not planned to be administered.

Summary statistics for each serum IgG antibody titer will be presented in the AIRI and a corresponding listing produced. Results for MMR titers will be summarized together irrespective of whether or not the infant received MMR vaccine. Analysis will be presented for the following subgroups:

- Maternal OCR exposure prior to the study in 3-month interval of before/during pregnancy (3-6 prior LMP, 0-3 month prior to LMP, 1st trimester)
- Type of feed: exclusive breast milk from birth to Month 6 vs others (including complementary feeding [breastmilk + formula milk, in various proportions] and formula feeding [no breast milk])
- Women with/without receiving postpartum ocrelizumab

A listing with all immune responses will be produce.

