4.5.3.1 Infant Positive Antibody Immune Response

The proportion of infants with positive humoral response (seroprotective titers as defined for the individual vaccine) will be presented for each individual IgG antibody titer in infants in the AIRI population. Analysis will be presented for all infants as well as by subgroups defined in Section 4.5.3.

A corresponding listing will be produced.

Vaccine test	Seroprotective Titer
Bordetella pertussis antibodies, IgG	> 1.04 COI
Haemophilus influenzae B, IgG	≥ 0.15 µg/mL
Anti-Diphtheria IgG(-70)CL	≥ 0.01 IU/mL
Anti-Tetanus Toxoid IgG(-70)RUO	≥ 0.01 IU/mL
13 Valent anti-pneumococcal antibody panel	≥ 0.35 µg/mL
Anti-Measles Vir IgG(-70)CL	≥ 120 mIU/mL
Anti-MumpsAT Vir iGG(-70)CL	≥ 17 U/mL
Anti-Rub Vir IgG(-70)RUOCL	≥ 10 IU/mL
anti-HBs	≥ 10 mIU/mL

Seroprotective titers are defined for each vaccine in the table below:

COI=Cut-off Index; IU=International Unit IgG=immunoglobulin G. Source: Storsaeter et al. 1998; European Medicines Agency 2015 For Tetanus and Diphtheria, a sensitivity analysis will be conducted using a seroprotective threshold of ≥ 0.1 IU/mL for infants receiving a 4th dose at least one month prior to the titer assessment. The ≥ 0.01 IU/mL threshold will still be used for those only receiving 3 doses.

4.5.4 Women's Ocrelizumab Levels during Pregnancy

To evaluate the levels of ocrelizumab in the mother during pregnancy, serum levels of ocrelizumab are measured during pregnancy (Week 24-30 and Week 35) and at delivery (within 24 hours after delivery). Summary statistics for the serum concentration of ocrelizumab in the women will be presented in the FASW. Analysis will also be presented for subgroups based on OCR exposure prior to the study as list below:

- In 3-month interval of before/during pregnancy (3-6 months before LMP, 0-3 months before to LMP, during the 1st trimester)
- ≥3 months before to LMP vs <3 months prior to LMP and/or during pregnancy

Serum concentration of ocrelizumab reported as BLQ will be imputed to zero for the calculation of summary statistics.

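### MMR titers are pooled whether or not the infant received MMR, so the MMR figures mix vaccine response with vaccine coverage

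*SAP*

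**What the plan says.** The secondary objective in Protocol Section 2 is whether potentially exposed infants are "able to mount humoral immune responses to clinically relevant vaccines". The endpoints are mean titers and the proportion with seroprotective titers.

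Protocol 3.1.4 times the infant sample one month after the first or second MMR dose, depending on the age at first dose, "or at Month 13 of chronological age (+30 days), if MMR vaccine is not planned to be administered". Infants without MMR are therefore an expected, sampled group.

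The SAP handles them as follows:

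- **Titers (SAP 4.5.3):** "Results for MMR titers will be summarized together irrespective of whether or not the infant received MMR vaccine".
- **Seroprotected proportion (SAP 4.5.3.1):** it "will be presented for each individual IgG antibody titer in infants in the AIRI population". A positive response is a titer cut-off: measles ≥ 120 mIU/mL, mumps ≥ 17 U/mL, rubella ≥ 10 IU/mL.
- **Analysis set, AIRI (SAP 4.1.5):** "all infants in the SAFI for whom any serum titers of antibody immune response to vaccinations are available". It has no condition on vaccine receipt, number of doses or time since the last dose.
- **Subgroups (SAP 4.5.3, reused in 4.5.3.1):** maternal exposure interval, type of feeding and postpartum ocrelizumab. Infant vaccination status is not among them.

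SAP Section 4 states that the SAP overrides the protocol where analyses differ.

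**The concern.** An infant who never received MMR cannot show a response to it. Under the plan that infant still enters the MMR titer summary. The seroprotection section does not repeat the pooling sentence, but its analysis set and cut-off rule lead to the same result. The reader of the planned tables cannot tell non-receipt from non-response.

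The mixing need not be random. Protocol 4.5.4 asks that vaccination be discussed with the mother, in particular vaccination with "live-attenuated vaccines (e.g., MMR) for which the results on B-cell levels at Week 6 of life may be informative". MMR receipt may thus depend on the primary endpoint. An infant with low B cells could go unvaccinated for that reason, and the pooled figure would show this as a poor vaccine response. That would suggest a link between B-cell depletion and vaccine failure which the data do not contain.

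**Working it through.** **Inputs**

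- Expected infants: SAP 2.2 gives 33 women and 10% dropout. 33 × (1 − 0.10) = 29.7, which reproduces the stated figure of about 30. I take n = 30 infants with titers as an assumption. Fewer are possible, because the Appendix 1 footnote on the post-MMR/Month 13 sample says: "However, if they cannot be collected, this will not be considered a protocol deviation".
- Interval method: two-sided Clopper-Pearson 95% (Protocol 6.4.2).
- u, the number without MMR; p_v, the proportion at or above the cut-off among vaccinated infants; p_u, the same among unvaccinated infants. None is in the documents, so all three are assumptions.

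**Step 1: how the plan counts each infant**

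| Infant | Below cut-off | At or above cut-off |
|---|---|---|
| Received MMR | not positive (informative) | positive (informative) |
| No MMR | counted as not positive (uninformative) | counted as positive (uninformative) |

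**Step 2: formula**

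Pooled proportion = [(n − u) × p_v + u × p_u] / n.

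Shift from the vaccinated proportion: p_v − pooled = (u/n) × (p_v − p_u).

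One infant of 30 contributes at most 1/30 = 3.3 points. If u = 0 the shift is zero.

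**Step 3: downward case (p_v = 100%, p_u = 0%)**

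| u | Pooled, as planned | Recipients only |
|---|---|---|
| 1 | 29/30 = 96.7% (82.8–99.9) | 29/29 = 100% (88.1–100) |
| 3 | 27/30 = 90.0% (73.5–97.9) | 27/27 = 100% (87.2–100) |
| 5 | 25/30 = 83.3% (65.3–94.4) | 25/25 = 100% (86.3–100) |

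With less extreme values, p_v from 70% to 100% and p_u from 0% to 10%, the difference p_v − p_u runs from 60 to 100 points. The shift is then (1/30) × 60 to 100 = 2.0 to 3.3 points for u = 1, and (3/30) × 60 to 100 = 6.0 to 10.0 points for u = 3.

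**Step 4: upward case**

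Suppose 24 of 27 vaccinated infants respond, 88.9% (70.8–97.6), and three unvaccinated infants are above the cut-off. Pooled: (24 + 3)/30 = 90.0%. A pooled 90.0% can therefore stand for a vaccinated response of 100% (Step 3, u = 3) or of 88.9%.

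**Step 5: subgroups**

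Take two exposure subgroups of 10 infants, p_v = 95% and p_u = 0% in both, with 0 unvaccinated in one and 3 in the other. Pooled: 10 × 0.95/10 = 95.0% against 7 × 0.95/10 = 66.5%. The gap of 28.5 points comes from coverage alone.

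**Step 6: mean titers**

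The same mixture applies. If the unvaccinated titer were zero, u = 3 would make the pooled arithmetic mean 27/30 = 90% of the recipients' mean.

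**The case against.** **The effect may be nil.** The documents give no MMR coverage figure. Protocol 4.5.3.2 expects every participating country to provide the relevant vaccines, and the Month 13 branch may be only a contingency. This stands as a limit on size. Supply to a country does not ensure that each infant is vaccinated, however, and the SAP sentence was written for the case where some are not.

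**The route through B cells is narrow.** If a low Week 6 result only delays MMR, the sample is delayed too, because it is timed from the dose. Such an infant is then measured after vaccination. This is correct and removes part of the selection argument. What remains is the infant for whom MMR is not planned at all.

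**Other antigens are not shown to be wrong.** The endpoint refers to doses given before 1 year, and Protocol 4.5.3.2 to vaccines administered locally, so the non-MMR titers can be read as tied to receipt. I accept this: for those antigens the request is a clarification. The explicit pooling rule concerns MMR only.

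**The tetanus and diphtheria rule is not a precedent for a denominator.** It is a sensitivity analysis with a higher threshold "for infants receiving a 4th dose at least one month prior to the titer assessment" and excludes nobody. That is right. It shows only that dose number and timing are usable in this analysis.

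**A recipients-only denominator is itself selected.** If low B cells make MMR less likely, recipients over-represent infants with normal B cells and response may be overstated. This is the strongest point, and it is why non-recipients must be shown beside recipients with their B-cell status. It does not justify counting non-recipients as responders or non-responders.

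**Listings allow reconstruction.** Titers are listed and vaccinations recorded, so a reader with the listings could rebuild the split by hand. The planned summary tables would still show the mixture.

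**Conclusion.** The concern holds. The pooling of titers is an explicit rule, and the seroprotected proportion follows it through the analysis set and the cut-off. As written, the MMR figures describe serostatus in a mixed group and are presented as vaccine response.

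The size depends wholly on how many infants lack MMR. It is zero if none do. With 30 infants it is up to 3.3 points for each unvaccinated infant below the cut-off, so 10.0 points for three if all vaccinated infants respond. The direction can reverse. These shifts are modest against the sampling error (the interval at 27/30 is 97.9 − 73.5 = 24.4 points wide), but they are systematic, can differ between exposure subgroups and cannot be seen in the planned tables.

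This is a descriptive secondary endpoint and no test depends on it. It should be corrected before the titer results are tabulated.

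**What to change.** Replace the pooling sentence in SAP 4.5.3 with:

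> *Measles, mumps and rubella titers and seroprotected proportions will be presented by vaccination status: (a) infants with at least one documented dose of a vaccine containing that antigen before the sample, with number of doses and dose-to-sample interval; (b) infants with no such dose, in a separate row with Week 6 B-cell status (below LLN: yes, no, missing).*

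Add to SAP 4.5.3.1:

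> *Row (a) is the main denominator for vaccine response. Infants in (a) sampled less than 1 month after the last dose will be flagged and shown separately.*

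An all-infant row may stay if it is labelled as serostatus irrespective of vaccination. Tabulate Week 6 B-cell status for both (a) and (b), so that any selection into vaccination is visible. For consistency, state the same received-vaccine denominator for the other antigens.

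**Cost:** SAP wording and one vaccination-status flag per antigen, derived from the infant vaccination records that Protocol 4.5.4 and the Schedule of Assessments already require. No new data are needed. Denominators become slightly smaller. Over-representation of infants with normal B cells in row (a) is made visible by the tabulation but is not removed.

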4.5.3.1 Infant Positive Antibody Immune Response

The proportion of infants with positive humoral response (seroprotective titers as defined for the individual vaccine) will be presented for each individual IgG antibody titer in infants in the AIRI population. Analysis will be presented for all infants as well as by subgroups defined in Section 4.5.3.

A corresponding listing will be produced.

Vaccine test	Seroprotective Titer
Bordetella pertussis antibodies, IgG	> 1.04 COI
Haemophilus influenzae B, IgG	≥ 0.15 µg/mL
Anti-Diphtheria IgG(-70)CL	≥ 0.01 IU/mL
Anti-Tetanus Toxoid IgG(-70)RUO	≥ 0.01 IU/mL
13 Valent anti-pneumococcal antibody panel	≥ 0.35 µg/mL
Anti-Measles Vir IgG(-70)CL	≥ 120 mIU/mL
Anti-MumpsAT Vir iGG(-70)CL	≥ 17 U/mL
Anti-Rub Vir IgG(-70)RUOCL	≥ 10 IU/mL
anti-HBs	≥ 10 mIU/mL

Seroprotective titers are defined for each vaccine in the table below:

COI=Cut-off Index; IU=International Unit IgG=immunoglobulin G. Source: Storsaeter et al. 1998; European Medicines Agency 2015 For Tetanus and Diphtheria, a sensitivity analysis will be conducted using a seroprotective threshold of ≥ 0.1 IU/mL for infants receiving a 4th dose at least one month prior to the titer assessment. The ≥ 0.01 IU/mL threshold will still be used for those only receiving 3 doses.

4.5.4 Women's Ocrelizumab Levels during Pregnancy

To evaluate the levels of ocrelizumab in the mother during pregnancy, serum levels of ocrelizumab are measured during pregnancy (Week 24-30 and Week 35) and at delivery (within 24 hours after delivery). Summary statistics for the serum concentration of ocrelizumab in the women will be presented in the FASW. Analysis will also be presented for subgroups based on OCR exposure prior to the study as list below:

- In 3-month interval of before/during pregnancy (3-6 months before LMP, 0-3 months before to LMP, during the 1st trimester)
- ≥3 months before to LMP vs <3 months prior to LMP and/or during pregnancy

Serum concentration of ocrelizumab reported as BLQ will be imputed to zero for the calculation of summary statistics.

4.6 EXPLORATORY ENDPOINTS

All exploratory analyses will be conducted using the SAFW or SAFI population as appropriate, unless otherwise specified.

4.6.1 Infants Growth Velocity

Infant growth velocity will be assessed by recording the infant's weight (kg), height (cm) and head circumference (cm) at birth, and Months 2, 4, 6, 9 and 12. The visit label will be derived based on infants actual age at the time of assessment: Month 2 (31-91 days), Month 4 (92-152 days), Month 6 (153-227 days), Month 9 (228-318 days), Month 12 (319-409 days), Month 13 (\geq 410 days).

Analysis will be based on the SAFI and includes:

- Actual values and change from baseline (defined as at birth) for weight, length/height, head circumference, and growth velocity (defined as the change from baseline divided by the number of months since baseline) will be summarized at each age time-point (birth, Months 2, 4, 6, 9, and 12).
- The weight-for-age and length/height-for-age percentiles and change from baseline percentiles at each time-point will be summarized.
- The number and percentage of infants in the 3rd, 5th, 10th, 25th, 50th, and >50th percentile of the WHO growth charts will be presented for weight-forage and length/height-for-age percentile at each time point. The number and percentage of infants within 10th-90th percentile, and 3rd-97th percentile of the WHO growth charts will also be presented.

- Shift tables will be presented for each parameter to compare the change from infant's percentile at baseline (≤3rd, >3rd ≤5th, >5th ≤10th, >10th ≤25th, >25th -≤50th, >50th) to each time-point (WHO 2006; WHO 2007; WHO 2017).
- Mean percentiles for weight-for age and length/height-for-age and corresponding 90% CIs will be plotted over time.
- Individual growth charts will be presented for each infant. This chart will
 present the weight and length/height for the infant over time, including
 reference lines for the 3rd, 25th, 50th, 75th, 90th and 97th percentiles for
 weight-for-age and length/height-for-age from WHO growth charts. Separate
 plots will be produces for each infant. Combined plots will also be produced for
 males and females separately, to show the trajectories of each infant on the
 same page.

All observed assessments will be included in the analysis; no imputation for missing assessments will be performed. The analysis will be based on the SAFI. Analysis will also be presented for the following subgroups:

- Type of feed: exclusive breast milk from birth to Month 6 vs others (including complementary feeding [breastmilk + formula milk, in various proportions] and formula feeding [no breast milk]).
- Maternal OCR exposure prior to the study in 3-month interval of before/during pregnancy (3-6 prior LMP, 0-3 month prior to LMP, 1st trimester)

All infant growth velocity data will be listed.

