Appendix 6 Time Windows for Infant Growth Velocity and Child Developmental Milestone Assessments

The following time windows must be applied for the assessment of growth velocity and child developmental milestones at Months 2, 4, 6, 9, and 12:

Timepoint	Associated time window
Month 2 ^a	1 month 0 days through 2 months 30 days
Month 4	3 months 0 days through 4 months 30 days
Month 6	5 months 0 days through 6 months 30 days
Month 9	9 months 0 days through 9 months 30 days
Month 12	11 months 0 days through 12 months 30 days

^a Where possible, the month 2 assessment can be combined with Visit 4 (Week 6 of life $[\pm 7 \text{ days}]$).

The following visualization depicts the timepoints and corresponding time windows based on the infant's month of age:

To calculate whether the infant falls under the respective assessment window based on its date of birth and weeks premature, the ASQ-3 age calculator can be used: https://agesandstages.com/free-resources/asq-calculator/. Note that an adjustment for premature birth will need to be made either manually or by using the calculator.

Assessment of growth velocity at Months 2, 4, 6, 9, and 12 must fall under the corresponding time windows of the ASQ-3; however, the date of assessment or data collection does not need to correspond to the same date of ASQ-3 assessment. Whenever possible, assessment of growth velocity may be collected as part of the infant's routine postnatal care visits performed by e.g., the pediatrician.

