4.6.2 Infants Childhood Developmental Milestones

The infant's developmental milestones will be assessed using the Ages and Stages Questionnaire version 3 (ASQ-3), in the domains of communication, gross motor, fine motor, problem solving, and personal-social at Week 6 and Months 2, 4, 6, 9, and 12.

The total score for each domain will be summarized by visit using continuous statistics in the SAFI. In addition, the number and percentage of infants with abnormal scores (Yes/No) will be presented in the SAFI, as per cut-offs below transcribed from the ASQ-3 User's guide.

450.2	Area				
questionnaire	Communication	Gross Motor	Fine Motor	Problem Solving	Personal Social
Month 2	22.77	41.84	30.16	24.62	33.71
Month 4	34.60	38.41	29.62	34.98	33.16
Month 6	29.65	22.25	25.14	27.72	25.34
Month 9	13.97	17.82	31.32	28.72	18.91
Month 12	15.64	21.49	34.50	27.32	21.73

ASQ-3=Ages and Stages Questionnaire version 3.

Values below the respective cut-off will be classified as abnormal (i.e., further assessment with a professional may be needed).

A corresponding listing will be produced.

Only questionnaires assigned to the correct time point will be included in the main analysis. If the wrong questionnaire is used for some time points in >20% infants, a sensitivity analysis will be performed with these data included.

4.6.3 Women's Immunity During Pregnancy

To evaluate humoral immunity to clinically relevant pathogens in mothers during pregnancy. Serum antibody (IgG) titers to immunizations: for measles, mumps, rubella, TT, diphtheria, pertussis, varicella zoster, Streptococcus pneumoniae, HBV and SARS-CoV-2 (along with nucleocapsid and spike protein titers; only for those mothers who have received the vaccine, as per local clinical practice) will be collected in the third trimester (Week 35). This will be presented in the same way as for infant immune response in Section 4.5.3 but for the SAFW population.

A listing with all immune response will be produce.

4.6.4 Women's Disease Activity

To assess disease activity and progression in women, the potential relapse is recorded and EDSS, a neurological examination is performed during pregnancy (Week 24-30 and Week 35), at infusion (if applicable), at early discontinuation and unscheduled visit if applicable. This will be summarized as follows in the FASW:

- Clinical Relapse:

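### The SAP labels growth visits by actual age, but the protocol times them by prematurity-adjusted age, so some compliant assessments of preterm infants fall under the next visit

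*SAP*

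**What the plan says.** **SAP 4.6.1 (growth).** "The visit label will be derived based on infants actual age at the time of assessment". The bands in days are "Month 2 (31-91 days), Month 4 (92-152 days), Month 6 (153-227 days), Month 9 (228-318 days), Month 12 (319-409 days), Month 13", the last open-ended from day 410. No correction for prematurity is mentioned. Summaries are planned at birth and Months 2, 4, 6, 9 and 12, so Month 13 exists as a label but not as a summary time point. All observed assessments are kept. No rule says which one to use when two carry the same label.

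**Protocol Appendix 6.** Windows are mandatory for both growth and the ASQ-3. The first, for Month 2, is "1 month 0 days through 2 months 30 days". The others, also inclusive of day 30 of their last month, start on completion of 3 months (Month 4, ending in the fifth month of age), 5 months (Month 6, ending in the seventh), 9 months (Month 9, ending in the tenth) and 11 months (Month 12, ending in the thirteenth). Growth assessments must lie inside the ASQ-3 windows, and "Note that an adjustment for premature birth will need to be made either manually or by using the calculator". The appendix does not say from which gestational age the adjustment is counted.

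**Links between the two.** Footnotes cc and dd of SAP Appendix 2 send the reader to protocol Appendix 6 for the growth and ASQ-3 windows. SAP 4.6.2 says "Only questionnaires assigned to the correct time point will be included in the main analysis" but does not define the correct time point.

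**The concern.** Sites schedule on one age scale and the analysis labels on another. The scales coincide for term infants. For a preterm infant, actual age exceeds adjusted age by the weeks of adjustment, so an assessment late in its protocol window can cross into the next SAP band.

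An example is a birth at 35 weeks with a 2-week (14-day) adjustment. An assessment at adjusted 2 months 25 days is at about day 86 adjusted (2 × 30.44 + 25) and day 100 actual, so it is labelled Month 4. The true Month 4 assessment at adjusted 4 months is at about day 122 adjusted and day 136 actual, and is also labelled Month 4. Month 2 is then empty and Month 4 holds two values with no rule for choosing.

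At stake are the visit-level means, percentile tables and shift tables. They are also reported by maternal exposure interval, where strata of a study with about 30 infants are small enough for one or two infants to show.

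**Working it through.** **Inputs.** SAP bands and protocol windows are as given above. The number of evaluable infants is about 30 (SAP 2.2), so 30 × 5 visits = 150 planned growth assessments. The only reference gestational age in the documents is 37 weeks, stated for B-cell sampling (protocol 3.3). The protocol's worked example is a birth at Week 35 sampled at Week 8 instead of Week 6, a 2-week shift (protocol 3.1.3).

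**Step 1: reproduce the SAP bands.** Midpoints between nominal Months 2, 4, 6, 9, 12 and 15 at 30.44 days per month are 3, 5, 7.5, 10.5 and 13.5 months = 91.3, 152.2, 228.3, 319.6 and 410.9 days. The SAP upper bounds are 91, 152, 227, 318 and 409, all within 2 days. The bands are simple midpoints on unadjusted age.

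**Step 2: share of compliant days that change label.** Let w be the weeks of adjustment. Actual age = adjusted age + 7w. If a protocol window ends at day B on adjusted age and is W days wide, and the next SAP label starts at day L, the mislabelled share is (B + 7w − L) / W, limited to between 0 and 1. For Month 2 at w = 2: B = 3 × 30.44 = 91.3, L = 92, W = 60.9, giving (91.3 + 14 − 92) / 60.9 = 13.3 / 60.9 = 22%.

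Counting calendar days over every birth date in one year gives:

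| w (weeks) | Month 2 | Month 4 | Month 6 | Month 9 | Month 12 | Mean |
|---|---|---|---|---|---|---|
| 0 (term) | 1.0% | 1.1% | 1.1% | 0% | 0% | 0.6% |
| 2 | 21.9% | 21.9% | 0.1% | 0.5% | 0.9% | 9.1% |
| 3 | 33.4% | 33.4% | 10.5% | 22.6% | 12.1% | 22.4% |
| 5 | 56.4% | 56.5% | 33.5% | 68.6% | 35.1% | 50.0% |

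The 3-week mean is 22 or 23%, depending on how month and day edges are treated. For w above 0 every mislabelled day moves to the later label. The shares assume that assessments are spread evenly over each window. If every assessment fell exactly on adjusted Month 2, 4, 6, 9 or 12, none would be mislabelled up to w = 4. At w = 5 and 6, Months 2 and 4 would be. From w = 7, all five would be.

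**Step 3: which w applies.** A birth at 35 weeks has w = 37 − 35 = 2 on the stated reference, or w = 40 − 35 = 5 if a 40-week reference is assumed. A birth at 34 weeks has w = 3 on the 37-week reference.

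**Step 4: scale.** As an assumption, take 9.8% preterm, a figure cited in protocol 1.3 for exposure before the LMP. Then 30 × 0.098 = 2.9 infants and 2.9 × 5 = 14.7 assessments. Mislabelled: 14.7 × 0.091 = 1.3 (w = 2), 14.7 × 0.224 = 3.3 (w = 3), 14.7 × 0.50 = 7.4 (w = 5). That is 1%, 2% and 5% of 150. Over the range w = 2 to w = 5, an assumed 5% preterm gives 0.7 to 3.8 assessments and 20% gives 2.7 to 15.0.

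**Step 5: Month 12.** On adjusted age the Month 12 window ends at about 13 × 30.44 = 396 days. At w = 5 an assessment at adjusted 12 months 20 days is at about day 365 + 20 + 35 = 420, so it is labelled Month 13 and leaves the summaries.

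**The case against.** Several points on the other side stand. The endpoint is exploratory and descriptive. No observation is discarded, all growth data are listed, and individual growth charts plot each infant over time without using labels. Velocity is change divided by months since birth, so the label does not alter it. Women with a previous preterm birth are excluded, which lowers the expected number of preterm infants. Actual age could also mean observed rather than nominal age, as in SAP 4.6.6, where it means ages not pooled into categories. On that reading the SAP still does not say whether age is chronological or corrected.

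SAP section 4 says that its analyses supersede the protocol's. This does not settle the matter, because sites still time visits by Appendix 6 and the SAP's own schedule points there.

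A reader might infer three stronger things that the documents do not support:

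- **That most or many preterm assessments are misplaced.** A share of half or more needs an adjustment of at least 5 weeks: a 40-week reference, which the documents do not give, or birth at 32 weeks or earlier on the 37-week one.
- **That the label makes WHO percentiles falsely low and suggests harm.** A percentile depends on the age used in the lookup, not on the visit label. SAP 4.6.1 does not say which age is used. Appendix 6 adjusts assessment windows and does not require corrected age for percentiles.
- **That correctly chosen ASQ-3 questionnaires will be dropped.** The actual-age rule appears only under growth, and SAP Appendix 2 directs the ASQ-3 to the adjusted windows. Dropping would occur only if the growth labels were reused.

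**Conclusion.** The mismatch in age basis is real and confined to preterm infants. Followed as written, SAP 4.6.1 places about 9% of their compliant days under the next label at a 2-week adjustment, 22 to 23% at 3 weeks and 50% at 5 weeks. With about 3 preterm infants of 30, that is roughly 1 to 7 of 150 assessments. These figures rest on even timing within windows, an assumed preterm share near 10%, and a reference gestational age that Appendix 6 leaves open. The 5-week figure for a 35-week birth needs an assumed 40-week reference.

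The damage is to visit-level summaries: duplicate labels, empty visits, and late Month 12 data moved to a label that is never summarised. It does not reach an infant's own velocity or the primary endpoint. It should still be corrected, because the rule contradicts the windows that sites are told to use.

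**What to change.** In SAP 4.6.1, add wording to this effect:

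> For infants born before 37 weeks, the visit label is derived from age adjusted for prematurity on the same basis as sites use under protocol Appendix 6, with reference gestational age [to be stated]. Chronological age is used for all other infants. If several assessments carry one label, the one closest to the nominal month is summarised. After birth, WHO percentiles for preterm infants are read at corrected age, with chronological age as a sensitivity analysis. The birth percentile of preterm infants is read as follows: [to be stated].

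The birth rule is needed because birth is the baseline for percentile change and the shift tables, and corrected age is negative at a preterm birth. Using corrected age for percentiles is an analysis choice, not something Appendix 6 requires.

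In SAP 4.6.2, define the correct time point by the adjusted Appendix 6 windows.

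With adjusted labels the mismatch for preterm infants falls to the term level (0.6% on average, at most 1.1% at any visit). The adjusted Month 12 window ends near day 396, inside the SAP band ending at day 409, so compliant Month 12 data no longer move to Month 13. The cost is a few sentences, a little programming and one sensitivity table. Gestational age at birth is already collected (protocol 4.5.3.1).
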